5.9.4 Shipping

[figure not shown]
******* DO NOT SHIP ON FRIDAY! *******

DO NOT LET PACKED COOLERS SIT AT AMBIENT TEMPERATURE FOR AN EXTENDED TIME PERIOD PRIOR TO FED EX PICK-UP

1. Assemble containers of food to be shipped: **FROZEN solid (at least OVERNIGHT at -20°C) prior to shipment.**
2. Ensure that each container is completely sealed.
3. Fill out a sample transfer form (#F001) for each cooler. Include all required information (see sample form included). Make a copy for your records.
4. Wrap **EACH** container of food in several layers of brown paper, newspaper, or other cushioning wrap. This is **necessary** in order to prevent container breakage during transit.
5. Place wrapped containers in the cooler, then pack wads of brown paper, newspaper or other cushioning material around each container. **NOTE: A maximum of six (6) containers may be shipped in one cooler. It is most efficient for FALCC if 6 menus per cooler are shipped.**
6. Place a layer of brown paper, newspaper, or other cushioning material on top of containers, then add a minimum of 5 pounds of dry ice. **USE CAUTION WHEN HANDLING DRY ICE; WEAR APPROPRIATE PROTECTIVE APPAREL AND INSULATED GLOVES.**
7. Pack wads of newspaper or brown paper to fill out cooler and prevent movement.
8. Place completed **sample transfer form (#F001)** and Deviation from SOP form(s) (Form #F002, if any) in a sealed zip-lock bag (to protect from moisture), and place in cooler, on top.
9. Tightly seal the lid of the cooler with packing tape as illustrated in Figure 1, (next page). For styrofoam coolers, seal the cooler around the seam as shown, then pack in the cardboard shipping box and seal the box with packing tape.
10. Fill out all information on the dry ice stickers (included in shipping kit) required for Federal Express shipping: Make sure to include your complete address and make sure that the dry ice weight agrees on all stickers for the same cooler.
11. Affix a pre-addressed pre-paid Fed-Ex shipping label to the box, and send via Federal Express overnight delivery to FALCC:
[name]
Dept. of Biochemistry
[name]
Virginia Tech
[name]
12. **Notify FALCC of shipment:** [contact] or [contact] or E-mail: [contact]

5.9.4.1 Figure 1

Illustration of Shipping Cooler

5.9.4.2 PROTOCOL 1 - FEEDING PERIOD 1

DELTA Sampling Plan for Assays
1993

COLOMBIA SEPT.

SUNDAY	MONDAY	TUESDAY	WEDNESDAY	THURSDAY	FRIDAY	SATURDAY
			1	2	3	4
5	6	7	8	9	10	11
12	13 Begin Run-in Diet A Menu 5	14 Diet B Menu 6	15 Diet C Menu 1	16 Diet A Menu 2	17 Diet B Menu 3	18
19	20 Diet C Menu 4	21 Diet A Menu 5	22 Diet B Menu 6	23 Diet C Menu 1	24 Diet A Menu 2	25
26	27 XX/3	28 XX/4 A-lo	29 XX/5 A-lo	30 XX/6 A-lo		

Key: Cycle # / Menu #
A-lo: Diet A, 1500 Kcal
Note: Do not sample cycle XX unless directed.

DELTA Sampling Plan for Assays
1993

COLOMBIA OCT.

SUNDAY	MONDAY	TUESDAY	WEDNESDAY	THURSDAY	FRIDAY	SATURDAY
					1 1 / 1 Begin Sampling	2 XX / W1 A-lo
3 XX / W2 A-lo	4 1 / 2 A	5 1 / 3 A	6 1 / 4 A	7 1 / 5 A	8 1 / 6 A	9 1 / W3 A
10 1 / W4 A	11 2 / 1 B-hi	12 2 / 2 B-hi	13 2 / 3 B-hi	14 2 / 4 B-hi	15 2 / 5 B-hi	16 2 / W1 B-hi
17 2 / W2 B-hi	18 2 / 6 B-hi	19 3 / 1 C-lo	20 3 / 2 C-lo	21 3 / 3 C-lo	22 3 / 4 C-lo	23 3 / W3 C-lo
24 3 / W4 C-lo	25 3 / 5 C-lo	26 3 / 6 C-lo	27 4 / 1 A-hi	28 4 / 2 A-hi	29 4 / 3 A-hi	30 4 / W1 A-hi
31 4 / W2 A-hi						

Key: Cycle # / Menu #
B-lo: Diet B, 1500 Kcal; B: Diet B, 2000 Kcal; C-hi: Diet C, 3000 Kcal; A: Diet A, 2000 Kcal
B-hi: Diet B, 3000 Kcal

DELTA Sampling Plan for Assays
1993

COLOMBIA NOV.

SUNDAY	MONDAY	TUESDAY	WEDNESDAY	THURSDAY	FRIDAY	SATURDAY
	1 4 / 4 A-hi	2 4 / 5 A-hi	3 4 / 6 A-hi	4 5 / 1 B-lo	5 5 / 2 B-lo	6 5 / W3 B-lo
7 5 / W4 B-lo	8 5 / 3 B-lo	9 5 / 4 B-lo	10 5 / 5 B-lo	11 5 / 6 B-lo	12 6 / 1 C	13 6 / W1 C
14 6 / W2 C	15 6 / 2 C	16 6 / 3 C	17 6 / 4 C	18 6 / 5 C	19 6 / 6 C	20 End of Period 1
21	22	23	24	25	26	27
28	29	30				

Key: Cycle # / Menu #
B-hi: Diet B, 3000 Kcal; C-lo: Diet C, 1500 Kcal; A-hi: Diet A, 3000 Kcal

PROTOCOL 1 - FEEDING PERIOD 1

**DELTA Sampling Plan for Beesys
1993**

SEPT.

PERRINGTON						
SUNDAY	MONDAY	TUESDAY	WEDNESDAY	THURSDAY	FRIDAY	SATURDAY
			1	2	3	4
5	6	7	8	9	10	11
12	13 Begin Run-in Diet A Menu 5	14 Diet B Menu 6	15 Diet C Menu 1	16 Diet A Menu 2	17 Diet B Menu 3	18
19	20 Diet C Menu 4	21 Diet A Menu 5	22 Diet B Menu 6	23 Diet C Menu 1	24 Diet A Menu 2	25
26	27 XX/3	28 XX/4 Begin Sampling B-lo	29 XX/5 B-lo	30 XX/6 B-lo		

Key: Cycle # / Menu #
B-lo: Diet B, 1500 Kcal

**DELTA Sampling Plan for Beesys
1993**

OCT.

PERRINGTON						
SUNDAY	MONDAY	TUESDAY	WEDNESDAY	THURSDAY	FRIDAY	SATURDAY
					1 / 1	2 XX / W1 B-lo
3 XX / W2 B-lo	4 1 / 2 B	5 1 / 3 B	6 1 / 4 B	7 1 / 5 B	8 1 / 6 B	9 1 / W3 B
10 1 / W4 B	11 2 / 1 C-hi	12 2 / 2 C-hi	13 2 / 3 C-hi	14 2 / 4 C-hi	15 2 / 5 C-hi	16 2 / W1 C-hi
17 2 / W2 C-hi	18 2 / 6 C-hi	19 3 / 1 A	20 3 / 2 A	21 3 / 3 A	22 3 / 4 A	23 3 / W3 A
24 3 / W4 A	25 3 / 5 A	26 3 / 6 A	27 4 / 1 B-hi	28 4 / 2 B-hi	29 4 / 3 B-hi	30 4 / W1 B-hi
31 4 / W2 B-hi						

Key: Cycle # / Menu #
B-lo: Diet B, 1500 Kcal; B: Diet B, 2000 Kcal; C-hi: Diet C, 3000 Kcal; A: Diet A, 2000 Kcal
B-hi: Diet B, 3000 Kcal

**DELTA Sampling Plan for Beesys
1993**

NOV.

PERRINGTON						
SUNDAY	MONDAY	TUESDAY	WEDNESDAY	THURSDAY	FRIDAY	SATURDAY
	1 4 / 4 B-hi	2 4 / 5 B-hi	3 4 / 6 B-hi	4 5 / 1 C-lo	5 5 / 2 C-lo	6 5 / W3 C-lo
7 5 / W4 C-lo	8 5 / 3 C-lo	9 5 / 4 C-lo	10 5 / 5 C-lo	11 5 / 6 C-lo	12 6 / 1 A-hi	13 6 / W1 A-hi
14 6 / W2 A-hi	15 6 / 2 A-hi	16 6 / 3 A-hi	17 6 / 4 A-hi	18 6 / 5 A-hi	19 6 / 6 A-hi	20 End of Period 1
21	22	23	24	25	26	27
28	29	30				

Key: Cycle # / Menu #
B-hi: Diet B, 3000 Kcal; C-lo: Diet C, 1500 Kcal; A-hi: Diet A, 3000 Kcal

PROTOCOL 1 - FEEDING PERIOD 1

DELTA Sampling Plan for Assays
1993

SEPT.

MINNESOTA							
SUNDAY	MONDAY	TUESDAY	WEDNESDAY	THURSDAY	FRIDAY	SATURDAY	
				1	2	3	4
5	6	7	8	9	10	11	
12	13	14	15	16	17	18	
	Begin Run-In Diet A Menu 5	Diet B Menu 6	Diet C Menu 1	Diet A Menu 2	Diet B Menu 3		
19	20	21	22	23	24	25	
	Diet C Menu 4	Diet A Menu 5	Diet B Menu 6	Diet C Menu 1	Diet A Menu 2		
26	27	28	29	30			
	XX/3	XX/4 Begin Sampling C-10	XX/5 C-10	XX/6 C-10			

Key: Cycle # / Menu #
C-10: Diet C, 1500 Kcal

DELTA Sampling Plan for Assays
1993

OCT.

MINNESOTA						
SUNDAY	MONDAY	TUESDAY	WEDNESDAY	THURSDAY	FRIDAY	SATURDAY
					1 / 1	2
					C	XX / W1 C-10
3	4	5	6	7	8	9
XX / W2 C-10	1 / 2 C	1 / 3 C	1 / 4 C	1 / 5 C	1 / 6 C	1 / W3 C
10	11	12	13	14	15	16
1 / W4 C	2 / 1 A-10	2 / 2 A-10	2 / 3 A-10	2 / 4 A-10	2 / 5 A-10	2 / W1 A-10
17	18	19	20	21	22	23
2 / W2 A-10	2 / 6 A-10	3 / 1 B	3 / 2 B	3 / 3 B	3 / 4 B	3 / W3 B
24	25	26	27	28	29	30
3 / W4 B 4 / W2 C-hi	3 / 5 B	3 / 6 B	4 / 1 C-hi	4 / 2 C-hi	4 / 3 C-hi	4 / W1 C-hi

Key: Cycle # / Menu #
C-10: Diet C, 1500 Kcal; C: Diet C, 2000 Kcal; A-10: Diet A, 1500 Kcal; B: Diet B, 2000 Kcal

DELTA Sampling Plan for Assays
1993

NOV.

MINNESOTA						
SUNDAY	MONDAY	TUESDAY	WEDNESDAY	THURSDAY	FRIDAY	SATURDAY
	1	2	3	4	5	6
	4 / 4 C-hi	4 / 5 C-hi	4 / 6 C-hi	5 / 1 A	5 / 2 A	5 / W3 A
7	8	9	10	11	12	13
5 / W4 A	5 / 3 A	5 / 4 A	5 / 5 A	5 / 6 A	6 / 1 B-hi	6 / W1 B-hi
14	15	16	17	18	19	20
6 / W2 B-hi	6 / 2 B-hi	6 / 3 B-hi	6 / 4 B-hi	6 / 5 B-hi	6 / 6 B-hi	End of Period 1
21	22	23	24	25	26	27
28	29	30				

Key: Cycle # / Menu #
C-hi: Diet C, 3000 Kcal; A: Diet A, 2000 Kcal; B-hi: Diet B, 3000 Kcal

PROTOCOL 1 - FEEDING PERIOD 1

DELTA Sampling Plan for Assays 1993

SEPT.

FEED STATE						
SUNDAY	MONDAY	TUESDAY	WEDNESDAY	THURSDAY	FRIDAY	SATURDAY
			1	2	3	4
5	6	7	8	9	10	11
12	13	14	15	16	17	18
	Begin Run-in Diet A Menu 5	Diet B Menu 6	Diet C Menu 1	Diet A Menu 2	Diet B Menu 3	
19	20	21	22	23	24	25
	Diet C Menu 4	Diet A Menu 5	Diet B Menu 6	Diet C Menu 1	Diet A Menu 2	
26	27	28	29	30		
	XX/3	XX/4 Begin Sampling A	XX/5 A	XX/6 A		

Key: Cycle # / Menu #
A: Diet A, 2000 Kcal

DELTA Sampling Plan for Assays 1993

OCT.

FEED STATE						
SUNDAY	MONDAY	TUESDAY	WEDNESDAY	THURSDAY	FRIDAY	SATURDAY
					1 / 1	2 XX / W1
					A-hi	A
3 XX / W2	4 1 / 2	5 1 / 3	6 1 / 4	7 1 / 5	8 1 / 6	9 1 / W3
A	A-hi	A-hi	A-hi	A-hi	A-hi	A-hi
10 1 / W4	11 2 / 1	12 2 / 2	13 2 / 3	14 2 / 4	15 2 / 5	16 2 / W1
A-hi	B-lo	B-lo	B-lo	B-lo	B-lo	B-lo
17 2 / W2	18 2 / 6	19 3 / 1	20 3 / 2	21 3 / 3	22 3 / 4	23 3 / W3
B-lo	B-lo	C	C	C	C	C
24 3 / W4 C	25 3 / 5	26 3 / 6	27 4 / 1	28 4 / 2	29 4 / 3	30 4 / W1
4 / W2 A-lo	C	C	A-lo	A-lo	A-lo	A-lo

Key: Cycle # / Menu # A: Diet A, 2000 Kcal; A-hi: Diet A, 3000 Kcal; B-lo: Diet B, 1500 Kcal;
C: Diet C, 2000 Kcal; A-lo: Diet A, 1500 Kcal

DELTA Sampling Plan for Assays 1993

NOV.

FEED STATE						
SUNDAY	MONDAY	TUESDAY	WEDNESDAY	THURSDAY	FRIDAY	SATURDAY
	1 4 / 4	2 4 / 5	3 4 / 6	4 5 / 1	5 5 / 2	6 5 / W3
	A-lo	A-lo	A-lo	B	B	B
7 5 / W4	8 5 / 3	9 5 / 4	10 5 / 5	11 5 / 6	12 6 / 1	13 6 / W1
B	B	B	B	B	C-hi	C-hi
14 6 / W2	15 6 / 2	16 6 / 3	17 6 / 4	18 6 / 5	19 6 / 6	20 End of Period 1
C-hi	C-hi	C-hi	C-hi	C-hi	C-hi	
21	22	23	24	25	26	27
28	29	30				

Key: Cycle # / Menu #
A-lo: Diet A, 1500 Kcal; B: Diet B, 2000 Kcal; C-hi: Diet C, 3000 Kcal

PROTOCOL 1 - FEEDING PERIOD 2

DELTA Sampling Plan for Assays
1994

COLUMBIA

JANUARY

SUN	MON	TUE	WED	THU	FRI	SAT
						1
2	3	4	5	6	7	8
9	10 3 / xx Begin Period 2	11 4 / xx	12 5 / xx	13 6 / xx	14 7 - 1 Abx	15 W1 / xx
16 W2 / xx	17 7 - 2 Abx	18 7 - 3 Abx	19 7 - 4 Abx	20 7 - 5 Abx	21 7 - 6 Abx	22 7 - W3 Abx
23 7 - W4 Abx	24 8 - 1 B	25 8 - 2 B	26 8 - 3 B	27 8 - 4 B	28 8 - 5 B	29 8 - W1 B
30 8 - W2 B	31 8 - 6 B					

DELTA Sampling Plan for Assays
1994

COLUMBIA

FEBRUARY

SUN	MON	TUE	WED	THU	FRI	SAT
		1 9 - 1 CM	2 9 - 2 CM	3 9 - 3 CM	4 9 - 4 CM	5 9 - W3 CM
6 9 - W4 CM	7 9 - 5 CM	8 9 - 6 CM	9 10 - 1 A	10 10 - 2 A	11 10 - 3 A	12 10 - W1 A
13 10 - W2 A	14 10 - 4 A	15 10 - 5 A	16 10 - 6 A	17 11 - 1 Bhd	18 11 - 2 Bhd	19 11 - W3 Bhd
20 11 - W4 Bhd	21 11 - 3 Bhd	22 11 - 4 Bhd	23 11 - 5 Bhd	24 11 - 6 Bhd	25 12 - 1 Cho	26 12 - W1 Cho
27 12 - W2 Cho	28 12 - 2 Cho					

DELTA Sampling Plan for Assays
1994

COLUMBIA

MARCH

SUN	MON	TUE	WED	THU	FRI	SAT
		1 12 - 3 Cho	2 12 - 4 Cho	3 12 - 5 Cho	4 12 - 6 End Period 2 Cho	5
6	7	8	9	10	11	12
13	14	15	16	17	18	19
20	21	22	23	24	25	26
27	28	29	30	31		

PROTOCOL 1 - FEEDING PERIOD 2

DELTA Sampling Plan for Assays
1994

P.B.R.C.

JANUARY

SUN	MON	TUE	WED	THU	FRI	SAT
						1
2	3	4	5	6	7	8
9	10 3 / xx Begin Period 2	11 4 / xx	12 5 / xx	13 6 / xx	14 7 - 1 Blo	15 W1 / xx
16 W2 / xx	17 7 - 2 Blo	18 7 - 3 Blo	19 7 - 4 Blo	20 7 - 5 Blo	21 7 - 6 Blo	22 7 - W3 Blo
23 7 - W4 Blo	24 8 - 1 C	25 8 - 2 C	26 8 - 3 C	27 8 - 4 C	28 8 - 5 C	29 8 - W1 C
30 8 - W2 C	31 8 - 6 C					

DELTA Sampling Plan for Assays
1994

P.B.R.C.

FEBRUARY

SUN	MON	TUE	WED	THU	FRI	SAT
		1 9 - 1 Blo	2 9 - 2 Blo	3 9 - 3 Blo	4 9 - 4 Blo	5 9 - W3 Blo
6 9 - W4 Blo	7 9 - 5 Blo	8 9 - 6 Blo	9 10 - 1 B	10 10 - 2 B	11 10 - 3 B	12 10 - W1 B
13 10 - W2 B	14 10 - 4 B	15 10 - 5 B	16 10 - 6 B	17 11 - 1 Chi	18 11 - 2 Chi	19 11 - W3 Chi
20 11 - W4 Chi	21 11 - 3 Chi	22 11 - 4 Chi	23 11 - 5 Chi	24 11 - 6 Chi	25 12 - 1 A	26 12 - W1 A
27 12 - W2 A	28 12 - 2 A					

DELTA Sampling Plan for Assays
1994

P.B.R.C.

MARCH

SUN	MON	TUE	WED	THU	FRI	SAT
		1 12 - 3 A	2 12 - 4 A	3 12 - 5 A	4 12 - 6 End Period 2 A	5
6	7	8	9	10	11	12
13	14	15	16	17	18	19
20	21	22	23	24	25	26
27	28	29	30	31		

PROTOCOL 1 - FEEDING PERIOD 2

DELTA Sampling Plan for Assays
1994

MINNESOTA

JANUARY

SUN	MON	TUE	WED	THU	FRI	SAT
						1
2	3	4	5	6	7	8
9	10 3 / xx Begin Period 2	11 4 / xx	12 5 / xx	13 6 / xx	14 7 - 1 Cb	15 W1 / xx
16 W2 / xx	17 7 - 2 Cb	18 7 - 3 Cb	19 7 - 4 Cb	20 7 - 5 Cb	21 7 - 6 Cb	22 7 - W3 Cb
23 7 - W4 Cb	24 8 - 1 Ab	25 8 - 2 Ab	26 8 - 3 Ab	27 8 - 4 Ab	28 8 - 5 Ab	29 8 - W1 Ab
30 8 - W2 Ab	31 8 - 6 Ab					

DELTA Sampling Plan for Assays
1994

MINNESOTA

FEBRUARY

SUN	MON	TUE	WED	THU	FRI	SAT
		1 9 - 1 Bb	2 9 - 2 Bb	3 9 - 3 Bb	4 9 - 4 Bb	5 9 - W3 Bb
6 9 - W4 Bb	7 9 - 5 Bb	8 9 - 6 Bb	9 10 - 1 C	10 10 - 2 C	11 10 - 3 C	12 10 - W1 C
13 10 - W2 C	14 10 - 4 C	15 10 - 5 C	16 10 - 6 C	17 11 - 1 Ab	18 11 - 2 Ab	19 11 - W3 Ab
20 11 - W4 Ab	21 11 - 3 Ab	22 11 - 4 Ab	23 11 - 5 Ab	24 11 - 6 Ab	25 12 - 1 B	26 12 - W1 B
27 12 - W2 B	28 12 - 2 B					

DELTA Sampling Plan for Assays
1994

MINNESOTA

MARCH

SUN	MON	TUE	WED	THU	FRI	SAT
		1 12 - 3 B	2 12 - 4 B	3 12 - 5 B	4 12 - 6 End Period 2 B	5
6	7	8	9	10	11	12
13	14	15	16	17	18	19
20	21	22	23	24	25	26
27	28	29	30	31		

PROTOCOL 1 - FEEDING PERIOD 2

DELTA Sampling Plan for Assays
1994

P.S.U.

JANUARY

SUN	MON	TUE	WED	THU	FRI	SAT
						1
2	3	4	5	6	7	8
9	10 3 / xx Begin Period 2	11 4 / xx	12 5 / xx	13 6 / xx	14 7 - 1	15 W1 / xx
16 W2 / xx	17 7 - 2	18 7 - 3	19 7 - 4	20 7 - 5	21 7 - 6	22 7 - W3
23 7 - W4	24 8 - 1	25 8 - 2	26 8 - 3	27 8 - 4	28 8 - 5	29 8 - W1
A	Blk	Blk	Blk	Blk	Blk	Blk
30 8 - W2	31 8 - 6					
Blk	Blk					

DELTA Sampling Plan for Assays
1994

P.S.U.

FEBRUARY

SUN	MON	TUE	WED	THU	FRI	SAT
		1 9 - 1	2 9 - 2	3 9 - 3	4 9 - 4	5 9 - W3
		Clc	Clc	Clc	Clc	Clc
6 9 - W4	7 9 - 5	8 9 - 6	9 10 - 1	10 10 - 2	11 10 - 3	12 10 - W1
Clc	Clc	Clc	AM	AM	AM	AM
13 10 - W2	14 10 - 4	15 10 - 5	16 10 - 6	17 11 - 1	18 11 - 2	19 11 - W3
AM	AM	AM	AM	Blc	Blc	Blc
20 11 - W4	21 11 - 3	22 11 - 4	23 11 - 5	24 11 - 6	25 12 - 1	26 12 - W1
Blc	Blc	Blc	Blc	Blc	C	C
27 12 - W2	28 12 - 2					
C	C					

DELTA Sampling Plan for Assays
1994

P.S.U.

MARCH

SUN	MON	TUE	WED	THU	FRI	SAT
		1 12 - 3	2 12 - 4	3 12 - 5	4 12 - 6 End Period 2	5
		C	C	C	C	
6	7	8	9	10	11	12
13	14	15	16	17	18	19
20	21	22	23	24	25	26
27	28	29	30	31		

PROTOCOL 1 - FEEDING PERIOD 3

DELTA Sampling Plan for Assays APRIL, 1994

COLUMBIA

SUN	MON	TUE	WED	THU	FRI	SAT
					1 GOOD FRIDAY	2
3	4 xx-3 Begin Per 3	5 xx-4	6 xx-5	7 xx-6	8 13-1 A-III	9 xx-W3
10 xx-W4	11 13-2 A-III	12 13-3 A-III	13 13-4 A-III	14 13-5 A-III	15 13-6 A-III	16 13-W1 A-III
17 13-W2 A-III	18 14-1 B-Ib	19 14-2 B-Ib	20 14-3 B-Ib	21 14-4 B-Ib	22 14-5 B-Ib	23 14-W3 B-Ib
24 14-W4 B-Ib	25 14-6 B-Ib	26 15-1 C	27 15-2 C	28 15-3 C	29 15-4 C	30 15-W1 C

KEY: A, B, C = 3000 Kcal
A-III, B-III, C-III = 3000 Kcal
A-Ib, B-Ib, C-Ib = 1500 Kcal

DELTA Sampling Plan for Assays MAY, 1994

COLUMBIA

SUN	MON	TUE	WED	THU	FRI	SAT
1 15-W2 C	2 15-5 C	3 15-6 C	4 16-1 A-Ib	5 16-2 A-Ib	6 16-3 A-Ib	7 16-W3 A-Ib
8 16-W4 A-Ib	9 16-4 A-Ib	10 16-5 A-Ib	11 16-6 A-Ib	12 17-1 B	13 17-2 B	14 17-W1 B
15 17-W2 B	16 17-3 B	17 17-4 B	18 17-5 B	19 17-6 B	20 18-1 C-III	21 18-W3 C-III
22 18-W4 C-III	23 18-2 C-III	24 18-3 C-III	25 18-4 C-III	26 18-5 C-III	27 18-6 C-III End of Study!	28
29	30 HOLIDAY!	31				

KEY: A, B, C = 3000 Kcal
A-III, B-III, C-III = 3000 Kcal
A-Ib, B-Ib, C-Ib = 1500 Kcal

PROTOCOL 1 - FEEDING PERIOD 3

DELTA Sampling Plan for Assays
APRIL, 1994

P.B.R.C.

SUN	MON	TUE	WED	THU	FRI	SAT
					1 GOOD FRIDAY	2
3	4 xx-3 Begin Per 3	5 xx-4	6 xx-5	7 xx-6	8 13-1 B-FH	9 xx-W3
10 xx-W4	11 13-2 B-FH	12 13-3 B-FH	13 13-4 B-FH	14 13-5 B-FH	15 13-6 B-FH	16 13-W1 B-FH
17 13-W2 B-FH	18 14-1 C-lb	19 14-2 C-lb	20 14-3 C-lb	21 14-4 C-lb	22 14-5 C-lb	23 14-W3 C-lb
24 14-W4 C-lb	25 14-6 C-lb	26 15-1 A-FH	27 15-2 A-FH	28 15-3 A-FH	29 15-4 A-FH	30 15-W1 A-FH

KEY: A, B, C = 3000 Kcal
A-FH, B-FH, C-FH = 3000 Kcal
A-lb, B-lb, C-lb = 1500 Kcal

DELTA Sampling Plan for Assays
MAY, 1994

P.B.R.C.

SUN	MON	TUE	WED	THU	FRI	SAT
1 15-W2 A-FH	2 15-5 A-FH	3 15-6 A-FH	4 16-1 B-lb	5 16-2 B-lb	6 16-3 B-lb	7 16-W3 B-lb
8 16-W4 B-lb	9 16-4 B-lb	10 16-5 B-lb	11 16-6 B-lb	12 17-1 C	13 17-2 C	14 17-W1 C
15 17-W2 C	16 17-3 C	17 17-4 C	18 17-5 C	19 17-6 C	20 18-1 A-lb	21 18-W3 A-lb
22 18-W4 A-lb	23 18-2 A-lb	24 18-3 A-lb	25 18-4 A-lb	26 18-5 A-lb	27 18-6 A-lb End of Study!	28
29	30 HOLIDAY!	31				

KEY: A, B, C = 3000 Kcal
A-FH, B-FH, C-FH = 3000 Kcal
A-lb, B-lb, C-lb = 1500 Kcal

PROTOCOL 1 - FEEDING PERIOD 3

DELTA Sampling Plan for Assays APRIL, 1994

MINNESOTA

SUN	MON	TUE	WED	THU	FRI	SAT
					1 GOOD FRIDAY	2
3	4 xx-3 Begin Per 3	5 xx-4	6 xx-5	7 xx-6	8 13-1 C-III	9 xx-W3
10 xx-W4	11 13-2 C-III	12 13-3 C-III	13 13-4 C-III	14 13-5 C-III	15 13-6 C-III	16 13-W1 C-III
17 13-W2 C-III	18 14-1 A	19 14-2 A	20 14-3 A	21 14-4 A	22 14-5 A	23 14-W3 A
24 14-W4 A	25 14-6 A	26 15-1 B-III	27 15-2 B-III	28 15-3 B-III	29 15-4 B-III	30 15-W1 B-III

KEY: A, B, C = 2000 Kcal
A-III, B-III, C-III = 3000 Kcal
A-Ia, B-Ia, C-Ia = 1500 Kcal

DELTA Sampling Plan for Assays MAY, 1994

MINNESOTA

SUN	MON	TUE	WED	THU	FRI	SAT
1 15-W2 B-III	2 15-5 B-III	3 15-6 B-III	4 16-1 C-Ia	5 16-2 C-Ia	6 16-3 C-Ia	7 16-W3 C-Ia
8 16-W4 C-Ia	9 16-4 C-Ia	10 16-5 C-Ia	11 16-6 C-Ia	12 17-1 A-III	13 17-2 A-III	14 17-W1 A-III
15 17-W2 A-III	16 17-3 A-III	17 17-4 A-III	18 17-5 A-III	19 17-6 A-III	20 18-1 B-Ia	21 18-W3 B-Ia
22 18-W4 B-Ia	23 18-2 B-Ia	24 18-3 B-Ia	25 18-4 B-Ia	26 18-5 B-Ia	27 18-6 B-Ia End of Study!	28
29	30 HOLIDAY!	31				

KEY: A, B, C = 2000 Kcal
A-III, B-III, C-III = 3000 Kcal
A-Ia, B-Ia, C-Ia = 1500 Kcal

PROTOCOL 1 - FEEDING PERIOD 3

DELTA Sampling Plan for Assays
APRIL, 1994

P.S.U.

SUN	MON	TUE	WED	THU	FRI	SAT
					1 GOOD FRIDAY	2
3	4 xx-3 Begin Per 3	5 xx-4	6 xx-5	7 xx-6	8 13-1 A-b	9 xx-W3
10 xx-W4	11 13-2 A-b	12 13-3 A-b	13 13-4 A-b	14 13-5 A-b	15 13-6 A-b	16 13-W1 A-b
17 13-W2 A-b	18 14-1 B	19 14-2 B	20 14-3 B	21 14-4 B	22 14-5 B	23 14-W3 B
24 14-W4 B	25 14-6 B	26 15-1 C-FH	27 15-2 C-FH	28 15-3 C-FH	29 15-4 C-FH	30 15-W1 C-FH

KEY: A, B, C = 2000 Kcal
A-FH, B-FH, C-FH = 3000 Kcal
A-b, B-b, C-b = 1500 Kcal

DELTA Sampling Plan for Assays
MAY, 1994

P.S.U.

SUN	MON	TUE	WED	THU	FRI	SAT
1 15-W2 C-FH	2 15-5 C-FH	3 15-6 C-FH	4 16-1 A	5 16-2 A	6 16-3 A	7 16-W3 A
8 16-W4 A	9 16-4 A	10 16-5 A	11 16-6 A	12 17-1 B-FH	13 17-2 B-FH	14 17-W1 B-FH
15 17-W2 B-FH	16 17-3 B-FH	17 17-4 B-FH	18 17-5 B-FH	19 17-6 B-FH	20 18-1 C-b	21 18-W3 C-b
22 18-W4 C-b	23 18-2 C-b	24 18-3 C-b	25 18-4 C-b	26 18-5 C-b	27 18-6 C-b End of Study!	28
29	30 HOLIDAY!	31				

KEY: A, B, C = 2000 Kcal
A-FH, B-FH, C-FH = 3000 Kcal
A-b, B-b, C-b = 1500 Kcal

5.10 UNIT FOOD SAMPLING

Scope

This procedure applies to collection of samples of unit foods for monitoring of diet composition as part of DELTA Protocol I (1993), Feeding Periods 2 and 3.

Purpose

To describe the procedure for collecting samples from unit food batches prepared for DELTA Protocol I and shipping the samples to FALCC as part of documenting the composition of experimental diets consumed during feeding trials.

Overview

Three unit foods (carrot muffin, banana muffin, bread) may be prepared for each of three diets (C, B, A). Each center chooses which unit foods to prepare, when they are prepared, and the size of batches. This protocol describes the documentation and sampling of unit food batches for analysis at the FALCC.

Each center will maintain a log of unit food batch preparation. Each center will randomly select two units from each batch of each unit food prepared for each diet throughout the study. These batch samples (2 units) will be individually packaged in zip-lock bags labeled with the center name, unit food name, diet, batch preparation date, and sampling date. All samples will be held at -20°C at the field center **until the end of each feeding period**, then shipped frozen on dry ice to the FALCC. At the FALCC, the samples will be composited and assayed according to the DELTA Protocol.

Materials

At Field Center:

unit food samples from all batches of all diets for entire feeding period
freezer (-20°C or lower)
heavy paper (e.g. brown paper or newspaper)
dry ice

Food Collection and Shipping Materials (supplied by FALCC):

Form #F031 (Unit Food Batch Preparation Log)
zip-lock bags
labels
cryogenic marker
fat-free powder-free gloves (disposable)
Form #F001 (sample transfer), with example form filled out
Forms #F002 (deviation from SOP)
shipping cooler
packing tape¹
Federal Express dry ice identification stickers
pre-addressed Federal Express shipping labels (1 per cooler)

PROCEDURES

NOTE: Follow these procedures exactly. If a deviation occurs in preparation, packaging, ingredients, sampling, shipping, etc., fill out form #F002 and include it with the food shipment.

TAKE THE SAME CARE SERVING AND PACKING FOODS FOR ASSAY AS YOU DO FOR FOODS FOR PATIENTS.

Receipt of Shipping Materials:

Make sure you received all items listed above. If there is a discrepancy or if you should need additional labels or supplies, immediately notify the FALCC at [contact], or [contact] or E-mail: [contact]

¹NOTE: The FALCC will supply each field center with a reasonable amount of packing tape for shipping foods to the FALCC - please reserve the tape for this use only.

SHIPPING

*** * * * * DO NOT SHIP ON FRIDAY * * * * ***

DO NOT LET PACKED COOLERS SIT AT AMBIENT TEMPERATURE FOR AN EXTENDED TIME PERIOD PRIOR TO FED EX PICK-UP

1. Assemble all samples to be shipped: **FROZEN solid (at least OVERNIGHT AT -20°C) prior to shipment.**
2. Ensure that each bag is completely sealed and properly labeled.
3. Fill out a sample transfer form (#F001). Include all required information (see sample form included); **there should be one entry for each sample enclosed in the cooler.** Make a copy of the form for your records.
4. Place all bags in the cooler, then pack wads of brown paper, newspaper or other cushioning, around them.

USE CAUTION WHEN HANDLING DRY ICE; WEAR APPROPRIATE PROTECTIVE APPAREL AND INSULATED GLOVES.

5. Place a layer of brown paper, newspaper, or other cushioning material on top of containers, then add a minimum of 5 pounds of dry ice.
6. Pack wads of newspaper on brown paper to fill out cooler and prevent movement.
7. Place completed sample transfer form (#F001), Deviation from SOP (Form(s) #F002, (if any), and a **copy** of the Unit food Batch Preparation Log (Form #F031) in a sealed zip-lock bag (to protect from moisture), and place in cooler, on top.
8. Tightly seal the lid of the cooler with packing tape around seam.
9. Fill out all information on the dry ice stickers (included i shipping kit) required for Federal Express shipping: Make sure to include your complete address and make sure that the dry ice weight agrees on all stickers for the same cooler.
10. Affix a pre-addressed pre-paid FedEx shipping label to the box, and send via Federal Express overnight delivery to FALCC:

[name]
Dept. of Biochemistry
[name]
Virginia Tech
[name]

11. **Notify FALCC of shipment:** [contact] or [contact] or E-MAIL: [contact]

Documentation of Unit Food Batch Preparation

The purpose of batch documentation is to ensure that all batches prepared are sampled and composited for assay. The "Unit Food Batch Preparation Log" serves this purpose.

1. At the time a batch of unit food is prepared, do the following:

Record the date of preparation, batch ID number (if any), the unit food name, diet, and batch size (e.g. total number of units or total weight), and your initials.

2. Maintain the preparation log at your center, and send a copy to the FALCC with the shipment of unit foods.

Food Collection

1. Wear fat-free powder-free gloves (supplied) while collecting foods.
2. For each batch of each type of unit food prepared for each diet throughout the feeding period, randomly select two (2) units and place them into a zip-lock bag.

i.e. There should be only two units in each zip-lock bag

3. For each sample (bag), enter the name of your Center, the unit food name, Diet (A, B, or C), batch preparation date, sampling date (=current date), and your initials into the appropriate spaces on a cryogenic label.
4. Affix label to each bag, **INSIDE**.

NOTE: It is very important to place the label inside the bag, as the label may detach at -20°C.

5. Seal each bag completely and check seal integrity.
6. Freeze and hold all samples at -20°C or lower prior to shipment.

Please return any unused labels and ziplock bags to the FALCC at the end of the feeding period (thank you).

5.11 UNIT FOOD SAMPLING AND ASSAY PLAN

Collection of Unit Food Samples

Each center will maintain a log of unit food batch preparation, which includes the date of preparation, unit food name, diet, and size of batch,. Each center will randomly select one unit from each batch of each unit food (i.e.; banana muffin, carrot muffin, bread) prepared. Each of these units will be individually packaged in an airtight zip-lock bag with the following: center name, unit food name, diet, and batch preparation date. The unit food samples for each feeding period will be held at -20°C at the field centers until the end of that feeding period, when they will be shipped frozen on dry ice to the FALCC along with a copy of the batch preparation log sheet.

Compositing

The FALCC will ensure that a sample has been received from each unit food batch (entered on the log sheet). Unit food composites will be prepared according to the following sampling plan;

	Period I			Period II			Period III		
	Time 1	Time 2	Time 3	Time 1	Time 2	Time 3	Time 1	Time 2	Time 3
Center 1	U(*,A)	U(*,B)	U(*,C)	U(*,B)	U(*,C)	U(*,A)	U(*,C)	U(*,A)	U(*,B)
Center 2	U(*,B)	U(*,C)	U(*,A)	U(*,C)	U(*,A)	U(*,B)	U(*,A)	U(*,B)	U(*,C)
Center 3	U(*,C)	U(*,A)	U(*,B)	U(*,A)	U(*,B)	U(*,C)	U(*,A)	U(*,B)	U(*,C)
Center 4	U(*,A)	U(*,B)	U(*,C)	U(*,A)	U(*,B)	U(*,C)	U(*,B)	U(*,C)	U(*,A)

There are a total of 12 unit food composites per feeding period. Each composite is prepared from three units of each type of unit food, randomly selected** from the collection of all batch samples of the unit foods prepared at the given center for the indicated diet during the specified time period (above). This means that the size of an individual composite would range from three units (only one type of unit food used) to 9 units (all three unit foods used).

Assay

Each unit food composite will be assayed for proximates (total fat, moisture, protein, ash). Total fat as a percent of kcal will be reported. The fat blends used for unit food preparation will be assayed separately for fatty acid composition.

*Indicates that the different unit foods would be combined into one composite (by diet, center, and time, above); A, B, and C denote the three different diets; Periods I, II, and III are the three Protocol I feeding periods; Times 1, 2, and 3 are specified timepoints, e.g., weeks 3, 5 and 7 of the period.

**All unit food sample bags for a given diet and time period will be mixed together and the three samples to be composited will be blindly selected.

CHAPTER 6
FOOD ANALYSIS

1

2

3

TABLE OF CONTENTS

6.0 FOOD ANALYSIS PROCEDURES	3
6.1 FOOD ANALYSIS LABORATORY CONTROL CENTER STANDARDS	10
6.1.1 Initial Log-in of Food Samples	10
6.1.2 Preparation of Diet Composites	13
6.1.3 Gravimetric Determination of Total Lipid in Foods	23
6.1.4 Extraction of Lipids from Foods with Chloroform-Methanol	27
6.1.5 Cholesterol Determination in Mixed Diets	30
6.1.7 Determination of Moisture in Diet Composites by Vacuum Oven Drying . .	36
6.1.8 GC Method for Fatty Acid Methyl Ester Analysis	39
CLASSIFICATION OF FATTY ACIDS	45
6.1.9 Determination of Ash in Diet Composites	46

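### The unit-food composite table in Section 5.11 gives the extra row to order A, B, C in all three periods, so diet and sampling time are avoidably (but only partly) associated

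*Protocol*

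**What the plan says.** Protocol Section 5.11 sets out a table of four centers by three periods by three times. Each cell names one diet, and a footnote to the table says of the asterisk: "Indicates that the different unit foods would be combined into one composite (by diet, center, and time, above". The times lie within a feeding period: "Times 1, 2, and 3 are specified timepoints, e.g., weeks 3, 5 and 7 of the period". The count is given as "There are a total of 12 unit food composites per feeding period".

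Centers 1 and 2 go through all three cyclic orders, one per period. Centers 3 and 4 do not. Their rows read "Center 3 U(*,C) U(*,A) U(*,B) U(*,A) U(*,B) U(*,C) U(*,A) U(*,B) U(*,C" and "Center 4 U(*,A) U(*,B) U(*,C) U(*,A) U(*,B) U(*,C) U(*,B) U(*,C) U(*,A".

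Section 5.10, which governs collection of these samples, is narrower: "This procedure applies to collection of samples of unit foods for monitoring of diet composition as part of DELTA Protocol I (1993), Feeding Periods 2". That sentence goes on to name only Period 3 as well. The Section 5.11 table includes Period I.

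**The concern.** The layout is plainly a rotation: every center-period row holds A, B and C once, and two of the four centers use each order exactly once over the study. The other two break the pattern with no reason given. Center 3 repeats A, B, C and never uses B, C, A. Center 4 repeats A, B, C and never uses C, A, B. This looks like a slip rather than a choice.

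A rotation of this kind prevents a change over time within a period from showing up as a difference between diets. Such a change is conceivable here. Under Section 5.10 each center decides which unit foods to make, when, and in what batch size. Samples also stay frozen at the center until the period ends, so early samples are stored longest. If the order is tilted the same way in every period, any such trend enters each diet's average with a different weight. At stake is the record of unit-food fat as a percent of energy for each diet.

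**Working it through.** **Inputs.** All come from the Section 5.11 table. The orders over Times 1, 2, 3 are:

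| | Period I | Period II | Period III |
|---|---|---|---|
| Center 1 | ABC | BCA | CAB |
| Center 2 | BCA | CAB | ABC |
| Center 3 | CAB | ABC | ABC |
| Center 4 | ABC | ABC | BCA |

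**The plan's own figure.** 4 centers × 3 times = 12 composites per period, as stated; × 3 periods = 36. Every row has nine cells and every center-period block contains each diet once, so the table does not appear damaged in extraction.

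**Use of each order.** ABC 6 rows, BCA 3, CAB 3. Within each period the split is 2/1/1, and the order used twice is ABC each time (Centers 1 and 4 in Period I, Centers 3 and 4 in Period II, Centers 2 and 3 in Period III).

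**Diet by time.** ABC puts A, B, C at Times 1, 2, 3; BCA puts B, C, A there; CAB puts C, A, B there. Hence:

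| Diet | Time 1 | Time 2 | Time 3 | Mean time index |
|---|---|---|---|---|
| A | 6 | 3 | 3 | (6×1 + 3×2 + 3×3)/12 = 1.75 |
| B | 3 | 6 | 3 | (3×1 + 6×2 + 3×3)/12 = 2.00 |
| C | 3 | 3 | 6 | (3×1 + 3×2 + 6×3)/12 = 2.25 |

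**Effect of a drift.** Assume a linear drift of d per time step, the same in all centers and periods. Compared with equal weighting of the times (mean index 2.00), the unadjusted mean is off by 0.25d for A, 0 for B and 0.25d for C in the opposite direction. A–C is off by (2.25 − 1.75)d = 0.5d and each adjacent comparison by 0.25d. The protocol gives no value for d. For illustration, d = 1 percentage point of energy would give 0.25 and 0.5 points.

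**Strength of the association.** The expected count per cell is 36/9 = 4. Chi-square = 3×(6−4)²/4 + 6×(3−4)²/4 = 4.5, so Cramér's V = √(4.5/(36×2)) = 0.25. On diet contrasts, information adjusted for time is 12 − 3²/12 = 11.25 against 12 unadjusted, an efficiency of 0.9375, or about 6% lost.

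**After changing two rows** (Period II Center 4 to CAB, Period III Center 3 to BCA): ABC 4, BCA 4, CAB 4. Every diet falls 4/4/4, every mean index is 2.00, V = 0, efficiency = 1, and each center uses each order once. The order used twice is ABC in Period I, CAB in Period II and BCA in Period III.

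**If only Periods II and III are sampled** (Section 5.10), there are 8 rows, and 8 is not divisible by 3.
- Current table: ABC 4, BCA 2, CAB 2. A falls 4/2/2 (mean 14/8 = 1.75) and C falls 2/2/4 (mean 18/8 = 2.25), so A–C is off by 0.5d.
- Changed table: ABC 2, BCA 3, CAB 3. A falls 2/3/3 (mean 17/8 = 2.125), B 3/2/3 (2.00) and C 3/3/2 (15/8 = 1.875), so A–C is off by 0.25d, with the sign reversed.

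**The case against.** The strongest reply is that nobody plans to compare unit-food fat between diets. Section 5.9 gives the purpose of assaying as verifying what participants were fed. Section 5.10 speaks of documenting composition. Section 5.11 asks only that fat as a percent of energy be reported. On that reading each diet is checked against its own target, and the relevant shift is at most 0.25d. This stands: the 0.5d figure matters only if someone compares A with C.

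The drift is also assumed. It would have to run in a broadly common direction across centers that bake on their own schedules, and nothing in the protocol suggests that it does. A change in the fatty acid profile of the fat blend would be caught elsewhere, because Section 5.11 has the blends assayed separately. An illustrative 0.25 to 0.5 points is small beside diets labelled 26%, 30% and 37% fat in the Section 5.7.7 substitution list. All of this stands.

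The protocol never promises balance over time, and a 2/1/1 split within one period cannot be avoided with four centers and three times. That is true, but it does not explain why the same order is doubled in every period when alternating it costs nothing.

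Three stronger readings are tempting and not supported. A reader might infer that diet and time are confounded outright; they are not, since every diet appears at every time and diet effects remain estimable after adjusting for time. A reader might infer that Center 4 is the culprit throughout; its Period III row is B, C, A, and the repeated row then belongs to Centers 2 and 3. A reader might infer that the diet effects on lipids or hemostatic factors are biased; this table governs only which food samples are pooled for assay.

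**Conclusion.** The point holds as a minor, avoidable imbalance in a table that the protocol itself fixes. The counts 6/3/3, 3/6/3 and 3/3/6 are exact and rest on no assumption. Their consequence does: under a common linear drift of d per time step, a diet's unadjusted unit-food mean is off by at most 0.25d and an A–C comparison by 0.5d. Without drift there is no bias, and adjusting for time removes a common drift at about 6% loss of efficiency. No primary endpoint is affected. It would also be too strong to say that a corrected table makes the bias zero in every case: that needs Period I to be sampled, on which Sections 5.10 and 5.11 disagree.

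**What to change.** In the Section 5.11 table, change Period II Center 4 to C, A, B and Period III Center 3 to B, C, A. Each diet is then composited four times at each time over 36 composites, and every center uses each order once. An equally good alternative changes three rows: Period II Center 4 to B, C, A; Period III Center 3 to B, C, A; Period III Center 4 to C, A, B.

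State in Sections 5.10 and 5.11 whether Period I unit foods are sampled. If they are not, keep the changed table, which halves the A–C imbalance, and report the diet means adjusted for time.

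The number of composites, units and assays is unchanged, so there is no added cost.
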